Phase 1 and Phase 2 measures will be used to achieve **2 Specific Aims**:

Aim 1. *To assess the acute effects of MEM (0 vs. 20 mg) on measures of early auditory information processing (EAIP) in patients with mild-to-moderate severity AD.* Measures of PPI, MMN and ASSR will be assessed in 88 individuals with mild-to-moderate severity AD after placebo (PBO) and 20 mg MEM po, in a double-blind, randomized order cross-over design. **Hypothesis 1:** Assessed across the full cohort of patients, PPI, MMN and ASSR will be significantly greater after MEM vs. PBO. However, the response to MEM will be heterogeneous: the magnitude of this “MEM effect” (MEM minus PBO) will vary across the dependent measures, and across patients, with some patients demonstrating robust increases in EAIP measures after MEM, and other demonstrating little response or reduced EAIP performance.

Aim 2. *To determine the ability of MEM-induced alterations in EAIP in AD patients to predict their clinical response to MEM.* The magnitude of the “MEM effect” will be calculated for each patient and each EAIP measure. MEM treatment will be initiated and titrated to 10 mg bid in all patients. Clinical severity will be assessed at baseline, 8, 16 and 24 weeks using the ADAS-cog as a primary measure. Analyses will determine whether the MEM effect on some or all EAIP measures moderates the magnitude of the clinical response to MEM. **Hypothesis 2:** Patients exhibiting a larger “MEM effect” on EAIP measures will exhibit a more robust positive clinical response to MEM, compared to patients exhibiting a smaller MEM effect on EAIP measures. This hypothesis will be tested empirically for each of the primary EAIP measures, and for regression-derived composite scores from multiple EAIP measures.

Analyses (linear mixed-effects model) will test the hypothesis (H2) that EAIP MEM sensitivity (in Phase 1) predicts the clinical response to MEM (in Phase 2). Moderating roles of specific variables on MEM sensitivity will be assessed, including demographic/clinical variables, baseline neuropsychological measures and genotypes associated with MEM sensitivity or AD. Source localization will identify anatomical substrates associated with MEM effects on EAIPs, and enable us to test structure- and circuit-based mediation models.

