A **comprehensive neuropsychological evaluation** is conducted under the supervision of [name] (\approx 2h; see "Human Subjects"). This test battery is used to characterize "MEM-sensitive" vs. "-insensitive" subgroups, and includes sensitive measures of memory (California Verbal Learning Test-II, WMS-IV Visual Reproduction Test with delayed recall and recognition, WMS-IV Logical Memory with delayed recall and recognition), attention (WAIS-R Digit Span Forward and Backward), language (Boston Naming Test; Letter and Category Fluency Tests), problem solving and executive function (modified Wisconsin Card Sort Test, Digit Symbol Substitution Test; Trailmaking, Fluency Switching, and Color-Word Interference subtests of the Delis-Kaplan Executive Functioning System [DKEFS]); constructional and visuospatial abilities (WASI-II Block Design Test, Clock Drawing Test, D-KEFS Visual Scanning), and global cognition (Mattis Dementia Rating Scale-2). Appropriate normative data are used for all tests (eg., Mayo Older American Normative Studies; 98). The number of prior cognitive assessments will be recorded for each subject to ensure that experimental groups (MEM-sensitive vs. MEM-insensitive) do not differ in the number of prior assessment exposures. A follow-up visit with the primary provider is scheduled for approximately 2-3 weeks after screening. All subjects are paid after screening, test days and 8, 16 and 24-week follow-ups (see "Human Subjects").

Test Days: Subjects who complete the **screening session** are scheduled for **EAIP Test Days** within 7 days. Transportation is provided. Urine toxicology is repeated on each test day. Test Days last from 0830–1600, much of which is spent relaxing, watching television, reading or eating. In brief, EAIP are assessed as in (59,99), 210 (PPI) and 345 min (MMN, ASSR) after administration of placebo or MEM (20 mg po), in a randomized order double-blind design. Vital signs (VS) and visual analog scale (VAS) measures of subjective self-ratings (99) are taken throughout the day. MEM pharmacokinetics are linear for single oral doses of 5-40 mg; T_{max} for a single 20 mg dose is 6.89 h; elimination $T_{(1/2)}$ is 60-80 h (94). Test days are \approx 1 week apart.

A.	\approx Day	B. Screen Day	C. Test Days a.m.	D. Test Days p.m.
Screen Day	1	Consent, Structured history	830: Brkfst, vital signs, UTox	VS, VAS cont'd
Test Day 1	8	Baseline clinical metrics	900: Pill (PBO or MEM)	1230: PPI (30 min)

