Aim 1 tests EAIP MEM sensitivity in patients with mild-to-moderate severity AD, in a double blind, within-subject cross-over design of MEM (20 mg po) vs. PBO. The primary result of Aim 1 is a biomarker characterization of "EAIP MEM-sensitivity" for each subject. Patients are also screened for baseline outcome and neurocognitive measures. In Aim 2, all patients titrate to 10 mg MEM bid, and outcome measures are collected at 8, 16 and 24 weeks. Analytic strategies are then used to test the hypothesis (H2) that greater EAIP MEM sensitivity predicts greater clinical MEM sensitivity.

Detailed Methods:

Stimulus parameters: The rationale for startle and ERP stimuli reflects both **empirical** and **theoretical** considerations, as discussed in our published reports (99,103). Empirically, these stimuli and session designs detect consistent MEM effects on PPI, MMN and ASSR (Fig. 2), and thus afford us the strongest predictions in terms of MEM effects in this application. There are also pragmatic considerations specific to each measure; for example, weaker pulse intensities generate smaller startle responses, and with the habituation resulting from repeated testing (2 test days), this results in an unacceptable number of startle "non-responders". Space does not allow a full description of the many such decision points with each measure, which are supported by a rich literature and the PI's and Co-PI's > 30 years of published experience.

Startle and PPI are assessed as in (99), with 42 trials, of 6 types: a 118 dB(A) 40 ms noise (pulse), and pulse preceded 10, 20, 30, 60, or 120 ms by a prepulse 16 dB over a 70 dB(A) background. Primary measure: **MEM effect (MEM minus PBO) on mean %PPI with 60 ms prepulse intervals**. Total time: 30 min, with clean-up.

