Aim 1: Repeated measure (Rm)-ANOVAs will determine whether PPI, MMN and ASSR significantly differ after MEM vs. PBO (Hypothesis 1). Primary variables for each EAIP, as well as exploratory "secondary" measures, are identified above. Based on a recruited sample of 88 total participants, we will have 80% power to detect effect sizes of $d = 0.35$ (small) using a Bonferroni corrected $\alpha = .05/3$ (2-tail). Heterogeneity of response will be characterized using variance components expressed as intraclass correlation coefficients (ICCs).

Aim 2: Linear mixed-effects models regressing change in ADAS-cog outcome scores (at 8, 16, and 24 weeks vs. baseline) onto a fixed effect of group defined by MEM sensitivity will test the hypothesis that patients exhibiting a larger "MEM effect" on EAIP measures will exhibit a larger positive clinical response to MEM. Groups will be defined by a median split of "MEM effect" (MEM minus PBO) on EAIP. Power was estimated using methods described by Hedeker et al. (25) solving for sample size with $\alpha = .05$ (2-tail), test-retest correlations of .50, and 5% attrition at each time point. A sample of 88 total participants provides us with 80% power to detect a medium effect of $d = 0.50$. The primary outcome will be chosen based on effect sizes obtained as part of Aim 1. In exploratory analyses, we will also examine group by time interactions using orthogonal polynomial contrasts. We will also predict change in clinical outcomes as a function of all four candidate biomarkers in order to create an optimal prediction equation. We will perform ROC curve analyses using EAIP MEM sensitivity values as continuous variables and predict clinical improvement after MEM as a discrete outcome (responders vs. non-responders) in order to determine the clinical utility of this approach defined in terms of sensitivity and specificity. Secondary analyses will also be conducted with biomarker groups defined as "MEM-sensitive vs. -insensitive" via specific thresholds for EAIP MEM sensitivity.

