Multiple analytic strategies: The critical test of H2 will utilize both continuous and discrete analyses. Treating EAIP MEM sensitivity as a **continuous variable** will enable us to identify moderating factors (i.e. factors moderating the relationship between EAIP MEM sensitivity and clinical MEM sensitivity) with greater power. By identifying these moderators, and their relative contributions to the biomarker-clinical response relationship, *this continuous approach will potentially be more informative regarding the mechanisms by which EAIP MEM sensitivity is related to MEM's clinical impact*. Compared to ANOVA, a linear mixed-effects model is also relatively less impacted by missing data.

Treating MEM sensitivity as a **discrete variable** will enable us to divide the patient sample via a specific threshold, eg. median split, based on EAIP MEM sensitivity (Fig. 3). Exploratory analyses will test more or less stringent thresholds, aiming to optimize the positive and negative predictive value of this discrete threshold. *This approach has the potential practical value of establishing preliminary criteria for distinct MEM-sensitive and MEM-insensitive clinical subgroups.*

Secondary / Exploratory Analyses: To test H2, we will examine multiple metrics of **EAIP MEM sensitivity**:

1. **primary** measures from each individual EAIP measure (described above);
2. **secondary** composite variable based on these 4 primary measures, generated via multiple regression;
3. **exploratory** measures of EAIP: P3a amplitude and RON (described above).

An underlying premise of H2 is that the neurobiological bases of MEM effects on the Aim 1 EAIP measures share some amount of variance, and hence positive and negative predictive value, with the clinical therapeutic response to MEM in AD. However, MEM effects on these 4 EAIP primary measures likely reflects its actions on (overlapping but) non-identical neural substrates; this is consistent with findings that MEM sensitivities on these measures are positively correlated for some (MEM effects on MMN and ASSR (65)) but not other measures (MEM effects on PPI and MMN (99)). *Which of these primary measures, or composite measure, provides the best prediction of MEM effects on AD-relevant neural substrates, and hence provides the best prediction of MEM's therapeutic sensitivity, is an important empirical question that we will address in Aim 2.*

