Sex as a biological variable: Sex will be included as a grouping factor in all major analyses; groups will be sex balanced as described in "Human Subjects". The PI was the first to report sex differences and menstrual cyclicity of PPI in HS (102), and some EAIP sex differences may persist into late life (48). No sex differences in **MEM effects** on PPI, MMN (99) or ASSR (65) were noted in our studies (Fig. 2).

Timeline (Table 2): Screening 114 subjects/57 mo. (2 subjects / mo.) is well within the capacity of our referral sources in the UCSD Memory and Geriatric Medicine Clinics, ADRC and affiliated community network (cumulative flow >>15 new AD patients/wk). Proposed EAIP testing rate (< 4 tests / mo.) is well within our capacity (typical rate 16 tests / mo.). Thus, subject recruitment and test rate should meet the demands of the proposed "N". EAIP methods are currently in use in our lab, so no new training, equipment or infrastructure is needed. At a rate of ≈1.5 completed subjects/mo., we will reach our target in 57 months, leaving 3 months for genotyping, data analysis and writing. Interim analyses at ≈6 months will confirm the fidelity of all measures and potentially adjust MEM test dose (see above), and at 36 months will guide a future NIA application.

Key benchmarks of success will include: 1. Recruitment and clinical and neurocognitive assessment of 88 individuals with Mild-to-Moderate AD (M:F ≈ 44:44). 2. Completion of two days of EAIP testing in study subjects, one week apart, in a double-blind, cross-over design using PBO vs. 20 mg MEM. 3. Titration of MEM to target dose (10 mg bid). 4. Repeated clinical and neurocognitive assessment after 8, 16 and 24 weeks of MEM treatment. 5. Completion of proposed analyses of EAIP and clinical data to test hypotheses, H1 and H2.

Potential Limitations:

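### The crossover analyses name no period or sequence term, so any day-to-day shift would sit in each patient's drug-minus-placebo score; a cheap wording change covers it

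*Combined protocol and SAP*

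**What the plan says.** All references are to the combined protocol and SAP.

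- **Design.** Specific Aims, Aim 1, has each patient tested on placebo and on 20 mg memantine "in a double-blind, randomized order cross-over design". Under Test Days, the elimination half-life "is 60-80 h (94). Test days are \approx 1 week apart".
- **Aim 1 analysis** (Statistical tests for each hypothesis): "Repeated measure (Rm)-ANOVAs will determine whether PPI, MMN and ASSR significantly differ after MEM vs. PBO (Hypothesis 1"). Also: "Heterogeneity of response will be characterized using variance components expressed as intraclass correlation coefficients (ICCs").
- **Aim 2 analysis** (same section): "Groups will be defined by a median split of" the memantine-minus-placebo difference. Under Multiple analytic strategies: "The critical test of H2 will utilize both continuous and discrete analyses".
- **Repeated testing.** Stimulus parameters, explaining why weaker startle pulses were rejected, refers to small responses together "with the habituation resulting from repeated testing (2 test days").
- **Covariates.** Sex as a biological variable: "Sex will be included as a grouping factor in all major analyses". No section gives test order the same treatment. The general statistical approach and the Aim 1 and Aim 2 paragraphs mention neither period nor sequence.

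**The concern.** In a two-period crossover, a general change from the first day to the second (habituation, familiarity, fatigue) enters the drug-minus-placebo score with one sign in patients who take memantine first and the other sign in those who take placebo first. In a balanced group mean the two cancel. In one patient's score they do not.

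This trial depends on the individual score. Aim 2 sorts patients by it, the ROC and threshold work uses it, and the Aim 1 heterogeneity summary describes its spread. The section on whether Aim 2 depends on Aim 1 calls that heterogeneity the key result for testing Hypothesis 2. If a shift exists and the models ignore it, part of what is labelled sensitivity to memantine is simply which day came first. Because order is randomised, this dilutes the Hypothesis 2 contrast; it cannot create one.

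**Working it through.** **Inputs from the documents.** N = 88. Aim 1: d = 0.35, two-sided alpha 0.05/3, 80% power. Aim 2: d = 0.50, correlation 0.50, 5% attrition per time point, 80% power. Half-life 60–80 h; test days about 168 h apart.

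**Assumed.** Equal sequences (44 and 44), a roughly normal score, and a shift of s SD of the score. The documents give no value for s, so a range is shown.

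**1. The plan's own figures.** Aim 1, paired t-test with 87 df: noncentrality 0.35 × √88 = 3.28, power 79.8%. Aim 2, repeated-measures two-group formula with three visits and retention 1, 0.95, 0.9025: 44.1 per group, about 88 in total. Both agree with the plan to rounding. Neither contains a period component.

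**2. Aim 1 with a shift.** The score moves by +s in one sequence and −s in the other. The mean is unchanged and the variance becomes 1 + s². Without a period term the effective size is 0.35/√(1 + s²). With the term the shift is removed and 86 df remain.

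| s | Effective d | Added score variance | Power, no term | Power, with term |
|---|---|---|---|---|
| 0 | 0.350 | 0% | 79.8% | 79.8% |
| 0.1 | 0.348 | 1% | 79.4% | 79.8% |
| 0.2 | 0.343 | 4% | 78.0% | 79.8% |
| 0.3 | 0.335 | 9% | 75.8% | 79.8% |

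**3. The pooled median split with a shift.** The chance of being called sensitive differs between orders by Φ(s) − Φ(−s). Patients moved across the median number 88 × (Φ(s) − 0.5). The Hypothesis 2 contrast is multiplied by exp(−s²/2).

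| s | Gap between orders | Patients moved, of 88 | d = 0.50 becomes |
|---|---|---|---|
| 0.1 | 8 points | 3.5 | 0.498 |
| 0.2 | 16 points | 7.0 | 0.490 |
| 0.3 | 24 points | 10.4 | 0.478 |

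**4. Hypothesis 2 power.** Simulation with 40,000 runs, n = 88 and a single outcome per patient. The score–outcome correlation is 0.365, chosen so that the pooled split has 80.0% power with no shift. Simulation error is about √(0.8 × 0.2/40,000) = 0.2 points.

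| s | Pooled split | Pooled split + sequence | Within-sequence split | Continuous | Continuous + sequence |
|---|---|---|---|---|---|
| 0 | 80.0% | 79.6% | 79.4% | 94.6% | 94.4% |
| 0.1 | 79.9% | 79.6% | 79.5% | 94.3% | 94.2% |
| 0.2 | 78.1% | 78.8% | 79.0% | 93.5% | 94.2% |
| 0.3 | 75.8% | 77.6% | 78.8% | 92.3% | 94.2% |

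The unadjusted split loses 0.1, 1.9 and 4.2 points. The sequence covariate recovers 0.7 points at 0.2 SD and 1.8 at 0.3 SD, and gives nothing back at 0.1 SD.

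**5. Carry-over, for scale.** Residual fraction at 168 h: 2^(−168/60) = 14.4% and 2^(−168/80) = 23.3%. Times 20 mg, that is 2.9 to 4.7 mg on the placebo day of patients given memantine first. If the effect were fully proportional to drug remaining (a worst case), Aim 1 d would be 0.35 × (1 − 0.144/2) = 0.325 to 0.35 × (1 − 0.233/2) = 0.309, and power 72.7% to 67.7%. A period term would not restore this.

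**The case against.** The strongest reply is that the documents argue against an order effect. The Significance section states that these measures suit repeated crossover testing, with no order or carry-over effect of note. The Fig. 2 results were obtained with a balanced crossover and the same 7-day gap. The habituation remark concerns startle amplitude and explains the choice of a strong pulse. The primary startle measure is a percentage reduction relative to the pulse-alone response, so a smaller startle need not shift it, and habituation is not mentioned for the EEG measures. At 0.1 SD the adjustment gains nothing for Hypothesis 2.

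Most of this stands, and it keeps the point small. It does not remove it. The Significance statement gives no estimate. The Fig. 2 results are group comparisons in healthy subjects and schizophrenia patients, and the second item under Potential Limitations concedes that age and diagnosis both differ here. The plan also puts sex in all major analyses although no sex difference in memantine effects was seen before, so a previous null result is not its own standard for leaving a factor out.

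Three stronger readings are tempting. One is that 14–23% of the dose on the placebo day makes the washout inadequate. The documents do not support this: the residual is 2.9–4.7 mg, and the section on the 20 mg dose reports 10 mg inactive on all three measures, albeit as group results in other populations. The second is that startle habituation shows the biomarker scores shift between days; no section shows that. The third is that Hypothesis 2 is biased towards a positive finding; randomised order rules that out.

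**Conclusion.** The omission is real: order is randomised, the score is used patient by patient, and no model names period or sequence. The consequence is modest. With balanced sequences the Aim 1 mean is unbiased. Over assumed shifts of 0.1 to 0.3 SD, the cost of leaving the terms out is 0.4 to 4.0 points of Aim 1 power (79.8% less 79.4% and 75.8%) and roughly 0 to 4 points for Hypothesis 2. The continuous test stays above 92% throughout.

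These sizes rest on the assumed shifts, equal sequences, a normal score and a single-outcome simplification of the mixed model. Carry-over is probably negligible and is not part of the case for change. Adopting the terms is worthwhile because it is ordinary crossover practice, costs almost nothing and guards against a larger shift in a population not yet studied this way. It is a nice-to-have improvement.

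**What to change.** Keep the 7-day gap and amend the analysis text.

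- **Aim 1.** Add period, with sequence, to the repeated-measures model, and report the memantine effect by sequence. Say that this adjusts for a period shift but cannot remove carry-over, which a two-period design cannot separate cleanly from sequence.
- **Aim 2.** Keep the pooled median split and add sequence as a covariate in the mixed model. Add it to the continuous model under Multiple analytic strategies too. The covariate adjusts the comparison; it does not re-sort patients whom a shift has moved across the median.
- **Sensitivity only.** Offer a within-sequence split, or scores centred within sequence, as a secondary check. These should not be primary. With essentially no shift they place about 4 of 88 patients differently by chance, and they give order-specific cutoffs that cannot be applied directly to a new patient's raw score, which is what the threshold and ROC work is meant to deliver.

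**Cost.** One or two degrees of freedom per model. Aim 1 power stays at 79.8%. If there is no shift, Hypothesis 2 loses about half a point (80.0% to 79.6% with the covariate). No visits, data or dosing change.

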Design Overview: The general study design is modeled after that employed by Peskind et al. (79) and Pomara et al. (81). These authors conducted a 24-week, multi-site placebo-controlled randomized trial of MEM monotherapy (10 mg bid) in mild-to-moderate AD, demonstrating significant gains in cognitive, global and behavioral measures. The present study will differ from that of Peskind et al. (79) in 3 major ways: 1. Patients will be characterized at baseline to assess their EAIP response to a MEM “challenge dose” (20 mg); 2. This is a single site study; 3. All patients will receive MEM treatment; to test the key hypothesis (H2), analyses will compare groups stratified by the magnitude of their EAIP response to MEM. Other minor methodological differences will be described below.

88 AD patients who consent to participation undergo a full neurocognitive characterization and medical evaluation. Patients also receive baseline ADAS-cog assessment and secondary outcome measures (described below) by [name] (Neuropsychologist; Clinic Director: UCSD Memory, Aging and Resilience Clinic [MARC]; Co-I).

Patients will then be tested in a PBO-controlled double-blind within-subject cross-over study of the effects of 20 mg MEM po on EAIP measures (PPI, MMN, ASSR). This proposed “N” is adequate to be stratified into “low” vs. “high” MEM sensitivity using discrete criteria, eg. median split, for categorical analyses (eg. ANOVA) and to detect medium effect size ($d=0.5$) differences in outcome between MEM-sensitive vs. -insensitive patients (see “Power Considerations”). Inclusion and exclusion criteria are seen in Table 2.

Table 1. Inclusion and exclusion criteria

Inclusion: 1. ADRC-confirmed diagnosis of AD; 2. **MMSE score 10-22**; 3. Age 50-70 y; 4. Knowledgeable caregiver; 5. Ambulatory; 6. Medically stable; 7. Audiometric testing (detection ≤ 40 db(A) at 1000 Hz); 8. Informed consent.

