1. Recruitment: One concern is the possible difficulty recruiting sufficient numbers of individuals with mild-to-moderate severity AD. A strength of this application is its intimate ties to active AD clinics and ongoing studies with large samples of well-characterized older adults, many of who have been diagnosed with AD, through collaborations with the UCSD Memory Clinic and Geriatric Medicine Outpatient Clinic, the UCSD ADRC and its affiliated networks throughout San Diego. Recruitment needs for this application are ≈ 2 new subjects / mo. (see "Timeline" and Table 2), with a projected 10% attrition at screening, and 5% attrition at each of the subsequent points of study contact (EAIP testing, weeks 8, 16 and 24), based on past experience and ongoing studies. The target population (mild-to-moderate AD) is not a focus of most ongoing UCSD studies, which prioritize MCI and Pre-MCI subjects; thus, availability of AD patients for this application will support much higher recruitment needs if attrition exceeds projected rates.

2. EAIP measures in AD patients: Our published reports of MEM effects on EAIP measures involved HS and SZ patients, ages 18-55 (65,99). The present application proposes such measures in patients with mild-to-moderate severity AD, ages 50-70 y; thus, both diagnosis and age of the proposed cohort differ from our past experience, and may present unexpected challenges. Importantly, our laboratory group has published extensively on EAIP measures across the full lifespan (eg. ages 18-88: (16)), and in populations with severe dementia and behavioral disturbances (eg. Huntington's Disease (104)), and recently completed a study of EAIP measures in 20 patients with mild-to-moderate severity AD ([name], PI). Thus, neither the clinical symptoms nor age of the proposed cohort should limit the acquisition or interpretation of EAIP measures.

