3. Expertise: The PI was Co-Director of the UCSD GHPP Clinic for 10 years (serving patients with Huntington's Disease (HD) and Hereditary Ataxias), and has been a clinically active Board Certified Psychiatrist for 24 years. While he has never had a primary role in AD clinical research, the PI brings to Aim 1 over 30 years of studies of EAIP measures, including studies of MEM effects on EAIP measures in rodents, HS and patients with SZ, and EAIP studies in patients with HD, Tourette Syndrome and other brain disorders (100,104). He has published extensively on the development, validation, interpretation and conceptual implications of EAIP measures as biomarkers in HS and patient populations (cf. 60-3,108). Importantly, the PI has assembled a team with expertise in AD, its assessment and treatment, and the conduct of clinical trials in AD. This team includes active Co-I's of Drs. [name], [name], [name] and [name], who collectively have significant expertise in these areas (see Biosketches) as well as the active collaboration of the leadership of the UCSD ADRC (Drs. [name] and [name]) and ADCS (Drs. [name] and [name]) (see Letters).

Table 2. Projected screening and completion "n"					
Study Month	12	24	36	48	57
Screen	24	48	72	96	114
EAIP Tests	21	43	64	86	103
Wk 8 measures	20	40	60	81	98
Wk 16 measures	19	38	57	77	93
Wk 24 measures	18	36	54	73	88

Protection of Human Subjects

(1) The final subject population for the present application will include approx. 88 adults, ages 50-70, carrying a diagnosis of AD, mild-to-moderate severity (based on a Mini-Mental Status Examination (MMSE) score of 10-22. Rationale for selection of this level of AD severity is discussed in the Research Strategy. The representation of males and females will be roughly equal; sample size is based on power analyses described above. We anticipate that, in order to complete testing in 88 subjects, we will need to "consent" and screen approximately 114 subjects; the remaining subjects will be excluded based on specific screening results, or self-initiated study withdrawal.

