Aim 2 involves treatment of all subjects with MEM monotherapy, in a manner (titration rate, final dose) that is common practice in clinical settings. This medication regimen has had longstanding FDA approval for use in moderate-to-severe AD; its use in mild-to-moderate severity AD as proposed here is both common community practice, and has been the focus on many large, multi-site studies (eg. 3,14,40-1,79,81,86). **There is no placebo control group or blinding during this phase, and no restrictions on medication adjustments based on clinical need, and thus none of the procedures are viewed to carry any added experimental risk beyond that encountered in standard community clinical practice.** Events that would preclude a participant from continuing with the intervention are based entirely on the clinical judgment of the patient's physician in consultation with the patient. There are no constraints on this process imposed by the study design. Subjects who finish baseline (T0) and biomarker (Aim 1) testing will be considered “valid”, and subjects who finish 8 weeks of MEM treatment and week 8 outcome measures will be considered “complete”.

Informed Consent Process: Informed Consent is conducted according to standard ADRC protocol, supervised by [name]. The consent process informs a subject about the study, indicates the participation is voluntary and he/she has the right to stop at any time. Risks are enumerated in the informed consent form and described orally during the consent process. The PI has successfully conducted Informed Consent with study subjects for over 25 consecutive years of NIH-funded studies.

INTERIM ANALYSIS

Interim analyses after 6 subjects will assess visual analog scales for subjective drug effects during Aim 1 and potentially adjust MEM test dose as described in the Research Strategy should unanticipated effects (e.g. sedation) be evident. Interim analyses of Aim 1 biomarker data at \approx 6 months (expected n=18) will confirm the fidelity of all EAIP measures, and at \approx 36 months (expected n=54) will guide a future NIA application. **Because the critical test of H2 does not involve an absolute magnitude of clinical change in the subject group, or even a statistically significant group change, there are no plans to stop the study based on an interim analysis demonstrating either outcome.**

DATA AND SAFETY MONITORING

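### Table 2 applies three of the four stated 5% losses, so 114 screened gives about 84 patients at week 24, not 88; the stage of the 88 and the interim sizes also need restating

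*Combined protocol and SAP*

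**What the plan says.** All references are to the combined protocol and SAP.

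**Where 88 is used**

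- Design Overview, as the number who consent: "88 AD patients who consent to participation undergo a full neurocognitive characterization".
- Statistical tests, Aim 1, as the recruited sample: "Based on a recruited sample of 88 total participants". This is said to give 80% power for d = 0.35 at two-sided alpha .05/3.
- Statistical tests, Aim 2: "A sample of 88 total participants provides us with 80% power to detect a medium effect of $d = 0.50", with alpha .05 two-sided, test-retest correlation .50 and 5% attrition at each time point.
- Key benchmarks of success: "Recruitment and clinical and neurocognitive assessment of 88 individuals with Mild-to-Moderate AD".
- Fig. 9 caption and the last row of Table 2: 88 is the final sample, with week-24 measures.
- Protection of Human Subjects (1): "in order to complete testing in 88 subjects, we will need to" consent and screen approximately 114.

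**Attrition.** Potential Limitations, item 1 (Recruitment), projects 10% at screening and "5% attrition at each of the subsequent points of study contact (EAIP testing, weeks 8, 16 and 24". Table 2 at month 57 reads: screened 114, EAIP tests 103, week 8 98, week 16 93, week 24 88.

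**Interim looks.** The Interim Analysis section plans a look at Aim 1 biomarker data at about 6 months ("expected n=18) will confirm the fidelity of all EAIP measures") and another at about 36 months with an expected 54. The Timeline gives screening of 114 subjects over 57 months, 2 per month.

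**The concern.** Three statements about sample size do not fit together.

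1. The text names four points at which 5% are lost after screening. Table 2 has three such steps, so its bottom line is too high on the stated rates.
2. With non-zero attrition, one number cannot be the consented, the recruited and the week-24 sample at once. The Aim 2 power paragraph treats 88 as a number to which attrition is applied; Table 2 treats it as what remains after attrition.
3. The interim looks concern Aim 1 (EAIP) data, but their sizes match a different row of Table 2.

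At stake is knowing when enrolment is finished, which sample each power statement describes, and how much data the interim looks will have. A team that took the Design Overview, the power section and the benchmark literally could stop too early.

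**Working it through.** **1. Reproducing Table 2.** Inputs: 114 screened (Table 2, Timeline); 10% and 5% losses (Potential Limitations, item 1).

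One 10% loss and three 5% losses give 114 × 0.90 × 0.95³ = 87.97. Step by step this is 102.6, 97.5, 92.6, 88.0, which is Table 2's 103, 98, 93, 88.

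**2. Applying all four stated losses.** 114 × 0.90 × 0.95⁴ = 83.57.

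| Stage | Four losses | Table 2 |
|---|---|---|
| Screened | 114 | 114 |
| After screening loss | 102.6 | not shown separately |
| EAIP tested | 97.5 | 103 |
| Week 8 | 92.6 | 98 |
| Week 16 | 88.0 | 93 |
| Week 24 | 83.6 | 88 |

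Rounding does not explain the gap: rounding to whole patients at every step gives 103, 98, 93, 88, 84. If 103 is read as patients entering EAIP testing, the EAIP loss falls between 103 and 98 and the week-24 loss is the one left out; the end is again about 84.

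**3. Screening needed for 88 at week 24.** 0.90 × 0.95⁴ = 0.7331, and 88 / 0.7331 = 120.05, so about 120. At 2 per month that is 60 months, against the 57 months of accrual plus 3 months for genotyping, analysis and writing in the Timeline.

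**4. Interim sizes.** Table 2's week-24 row reads 18 at month 12 and 54 at month 36, the two figures in the Interim Analysis section. Its EAIP row reads 21 and 64. Table 2 has no 6-month column, so I interpolate at 2 screened per month: 12 screened by month 6 and 72 by month 36.

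- EAIP loss applied (0.90 × 0.95 = 0.855): 12 × 0.855 = 10.3 and 72 × 0.855 = 61.6.
- Table 2's EAIP row kept: 12 × 0.90 = 10.8 and, from the table, 64.

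Eighteen tested exceeds even the 12 screened by month 6.

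**5. Power, Aim 1.** Paired t-test, noncentral t, d = 0.35, two-sided alpha .05/3.

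- 88 tested pairs: 79.8%. This reproduces the stated 80%, so here 88 has to mean patients tested.
- 97 tested (114 screened, four losses): 84%.
- 75 tested (88 consented: 88 × 0.90 × 0.95 = 75.2): 72%.

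**6. Power, Aim 2.** The plan cites a method without giving the formula. I assume a time-averaged two-group contrast over weeks 8, 16 and 24 with correlation 0.5 and monotone dropout. A patient with k visits contributes k / (1 + 0.5(k − 1)), that is 1, 1.333 or 1.5 for one, two or three visits. With I the sum over patients, power = Φ(0.5 × √(I/4) − 1.96).

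- Four-loss flow (92.6, 88.0, 83.6): I = 83.57 × 1.5 + 4.40 × 1.333 + 4.63 × 1 = 135.9; power = Φ(2.914 − 1.96) = 83%.
- Table 2 flow (98, 93, 88): 85%.
- 88 starting, 5% lost by each of the three visits (83.6, 79.4, 75.4): 79%. With the first loss only after week 8 it is 81%. On this method 88 therefore fits a starting number with attrition built in.
- 88 consented, all losses (71.5, 67.9, 64.5): 73%.

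**The case against.** **The plan does not stop at 88 consented.** The Timeline says 114 are to be screened, Protection of Human Subjects (1) ties 114 consented to a final 88, and Table 2 runs from one to the other. A reader might infer from the Design Overview and the power section that the trial is underpowered. The documents do not support that: the 72% and 73% figures describe only a literal stop at 88 consented, and with 114 screened both aims stay above 80% even after all four losses. This objection stands in full.

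**Eighty-four is not a shortfall in completers.** The section on incomplete or discontinued subjects calls a patient complete after 8 weeks at the target dose and puts such patients in the primary Aim 2 analysis. Protection Against Study Risks likewise uses 8 weeks of treatment plus the week-8 measures. On the four-loss chain about 93 patients reach week 8. This also stands: the gap concerns the week-24 sample only.

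**The attrition list may be the slip.** Table 2, the 114 and the final 88 agree with one another; the bracketed list of four contacts is the odd one out. That is possible, and the documents do not settle it. The figure of 84 is therefore conditional on the list being meant as written.

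**The gap is small and there is slack.** The counts are projections (about 88, about 114), and the recruitment section says referral sources could support much higher needs if attrition is worse than projected. That covers roughly 6 extra patients screened. It does not remove the contradiction, and it does not touch the 6-month interim size, which fails on the plan's own accrual rate.

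**Conclusion.** The sample-size figures are inconsistent as written. On the stated losses, 114 screened gives about 84 patients with week-24 data, 4 fewer than Table 2 shows, and 88 would need about 120 screened. The figure 88 is attached to stages that cannot all have the same count. The interim size of 18 at about 6 months is unattainable at 2 screened per month, and the 54 at about 36 months is a week-24 count used for EAIP data.

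This is a fault of definition and bookkeeping. It does not show a loss of power: with 114 screened and all four losses, Aim 1 power is about 84% (97 tested, d = 0.35) and Aim 2 power about 83% (d = 0.50). The chain assumes multiplicative losses. The Aim 2 figure also rests on the assumed reading of the cited method, and the 6-month counts on steady accrual with no lag between screening and testing.

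**What to change.** 1. Make the attrition list in Potential Limitations, item 1, agree with Table 2. If four losses are meant, restate Table 2 at month 57 as 114 screened, about 103 after screening, 97 EAIP tested, 93 at week 8, 88 at week 16 and 84 at week 24, rework its earlier columns, and change the final 88 in Fig. 9 and Protection of Human Subjects (1); or keep 88 at week 24 and plan to screen about 120. If three losses are meant, correct the list.
2. In the Design Overview, the Aim 1 and Aim 2 power paragraphs and the benchmarks, replace 88 consented or recruited with the stage meant. State Aim 1 power at the number EAIP tested and Aim 2 power at the numbers expected at weeks 8, 16 and 24.
3. In Interim Analysis, give the EAIP-tested count on the reconciled chain: about 10 at 6 months and 62 at 36 months with the EAIP loss applied, or about 11 and 64 if Table 2's EAIP row is kept.
4. Call the last count the week-24 sample, since the plan already defines complete at week 8.

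The cost is wording and restated figures, with no change to design or analysis. Only the option of screening about 120 costs more: it would use the 3 months kept for genotyping, analysis and writing unless accrual exceeds 2 per month.
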